9.4.1.1 Criteria for Interruption of Treatment, Dose Reduction and Resumption of Treatment

Dose reduction and interruptions for subjects who experience toxicity will be made according to the guidelines provided in [Table 2](#).

Dose reductions will occur in succession based on the previous dose level (24, 20, 14, and 10 mg/day). Any dose reduction below 10 mg/day must be discussed with the sponsor. Once the dose has been reduced, it cannot be increased at a later date.

Table 2 Dose Reduction and Interruption Instructions for Lenvatinib-Related Toxicities

Treatment-Related Toxicity ^{a,b} including hepatic injury and thromboembolic events	Management	Dose Adjustment
Grade 1 and tolerable Grade 2		
	Continue treatment	No change
Intolerable Grade 2^c or Grade 3^{d,e}		
First occurrence	Interrupt until resolved to Grade 0-1 or baseline ^f	20 mg orally QD (one-level reduction)
Second occurrence (same toxicity or new toxicity)	Interrupt until resolved to Grade 0-1 or baseline ^f	14 mg orally QD (one-level reduction)
Third occurrence (same toxicity or new toxicity)	Interrupt until resolved to Grade 0-1 or baseline ^f	10 mg orally QD (one-level reduction)
Fourth occurrence (same toxicity or new toxicity)	Interrupt until resolved to Grade 0-1 or baseline ^f	Discuss with sponsor
Grade 4^g: Discontinue Study Treatment		

QD = once a day

Note: For grading, see Common Terminology Criteria for Adverse Events version 4.03. Collect all CTC grades of AEs, decreasing and increasing grade.

a: A delay of study treatment for more than 28 days (due to treatment-related toxicities) will require a discussion with the sponsor before treatment can be resumed.

b: Initiate optimal medical management for nausea, vomiting, and/or diarrhea prior to any study treatment, interruption, or dose reduction.

c: Grade 2 toxicities will be determined to be tolerable or intolerable by both the subject and investigator. If Grade 2 toxicity is determined to be intolerable, the dose of study drug will be reduced with or without dose interruption. Interruption for Grade 3 toxicities is mandatory.

d: Obese subjects with weight loss requiring dose interruption and reduction do not need to return to baseline or Grade 1 weight loss to restart lenvatinib. Based on the judgment of the investigator, subjects may be restarted at the lower dose of lenvatinib once the weight has been stable for at least 1 week. Normal BMI should be used as the new baseline for future dose reductions.

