e: Not applicable to abnormal clinical laboratory values that are not clinically relevant based on the judgment of the investigator (eg, ALT, AST, γ -GTP values $< 10 \times$ ULN, and Na).

f: For hematology toxicities, restart treatment after toxicity resolves to Grade 2.

g: Excluding laboratory abnormalities judged to be non-life-threatening, in which case manage as Grade 3.

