9.5.1.5.1 ADVERSE EVENTS AND EVENTS ASSOCIATED WITH SPECIAL SITUATIONS

An AE is any untoward medical occurrence in a patient or clinical investigation subject administered an investigational product. An AE does not necessarily have a causal relationship with the medicinal product. For this study, the study drug is lenvatinib.

The criteria for identifying AEs in this study are:

- Any unfavorable and unintended sign (including an abnormal laboratory finding), symptom, or disease temporally associated with the use of an investigational product, whether or not considered related to the investigational product (Note: Every sign or symptom should not be listed as a separate AE if the applicable disease [diagnosis] is being reported as an AE)
- Any new disease or exacerbation of an existing disease. However, worsening of the primary disease should be captured under efficacy assessments as disease progression rather than as an AE.
- Any deterioration in nonprotocol-required measurements of a laboratory value or other clinical test (eg, ECG or x-ray) that results in symptoms, a change in treatment, or discontinuation of study drug
- Recurrence of an intermittent medical condition (eg, headache) not present pretreatment (Baseline)
- An abnormal laboratory test result should be considered an AE if the identified laboratory abnormality leads to any type of intervention, withdrawal of study drug, or withholding of study drug, whether prescribed in the protocol or not

All AEs observed during the study will be reported on the CRF. All AEs, regardless of relationship to study drug or procedure, should be collected beginning from the time the subject signs the study ICF and for 28 days after the last dose of study treatment. Subjects who fail screening primarily due to AE(s) must have the AE(s) leading to screen failure

reported on the Screening Disposition CRF. SAEs will be collected for 28 days after the last dose.

Abnormal laboratory values should not be listed as separate AEs if they are considered to be part of the clinical syndrome that is being reported as an AE. It is the responsibility of the investigator to review all laboratory findings in all subjects and determine if they constitute an AE. Medical and scientific judgment should be exercised in deciding whether an isolated laboratory abnormality should be classified as an AE. Any laboratory abnormality considered to constitute an AE should be reported on the Adverse Event CRF.

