All hematology, blood chemistry, urinalysis, and pregnancy test (serum or urine) samples are to be obtained prior to study drug administration and results reviewed prior to administration/dispensing of study drug at the beginning of each treatment cycle. Refer to [Table 2](#) for the management of clinically significant laboratory abnormalities.

A laboratory abnormality may meet the criteria to qualify as an AE as described in this protocol (see Section [9.5.1.5.1](#) and the CRF Completion Guidelines. In these instances, the AE corresponding to the laboratory abnormality will be recorded on the Adverse Event CRF.

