- m. A comprehensive PE (including a neurological examination) will be performed at the Screening Visit, on Cycle 1/Day 15, on Day 1 of each subsequent cycle, and at the End of Treatment assessment. A symptom-directed PE will be performed on Baseline (Day -1) or on C1D1 prior to treatment, and at any time during the study, as clinically indicated.
- n. Single 12-lead ECG. Subjects must be in the recumbent position for a period of 5 minutes prior to the ECG.
- o. **For subjects who had prior anthracyclines**, an echocardiogram or MUGA scan will be performed during Screening Visit and at the End of Treatment Visit or sooner, if clinically indicated.
- p. Clinical chemistry and hematology results must be reviewed prior to administration of lenvatinib on C1D1 and within 48 hours after dispensing lenvatinib for all subsequent cycles. Scheduled assessments (Screen, Baseline, Cycle 1/Day 15, Day 1 of each subsequent cycle starting with Cycle 2 and at the End of Treatment Visit) may be performed within 72 hours prior to the visit. If there is a clinically relevant hematologic or clinical chemistry toxicity of \geq Grade 3, repeat laboratory test and AE assessment at least every 3 days (until improvement to $<$ Grade 3). An INR will be performed at screening/baseline and when clinically indicated.
- q. **On C2D15, only liver function (ALT, AST, alkaline phosphatase, total bilirubin, direct bilirubin) should be performed.** Note: liver function should be assessed

- every 2 weeks for the first two months (Baseline, C1D1, C1D15, C2D1, and C2D15) and then monthly thereafter (Day 1 of each subsequent cycle).
- r. Assessment of TSH and free T4 levels are to be performed at the Screening/Baseline Visit and then **every 2 cycles** (starting at Cycle 2) throughout the study.

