9.5.2.2 Description of Procedures/Assessments Schedule

Refer to [Table 4](#) for a description and timing of each procedure and assessment in the Prerandomization and Randomization Phase.

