11 PROCEDURES AND INSTRUCTIONS (ADMINISTRATIVE PROCEDURES)

11.1 Changes to the Protocol

Any change to the protocol requires a written protocol amendment or administrative change that must be approved by the sponsor before implementation. Amendments specifically affecting the safety of subjects, the scope of the investigation, or the scientific quality of the study require submission to health or regulatory authorities as well as additional approval by the applicable IRBs/IECs. These requirements should in no way prevent any immediate action from being taken by the investigator, or by the sponsor, in the interest of preserving the safety of all subjects included in the study. If the investigator determines that an immediate change to or deviation from the protocol is necessary for safety reasons to eliminate an immediate hazard to the subjects, the sponsor's medical monitor and the IRB/IEC for the site must be notified immediately. The sponsor must notify the health or regulatory authority as required per local regulations.

Protocol amendments that affect only administrative aspects of the study may not require submission to health or regulatory authority or the IRB/IEC, but the health or regulatory authority and IRB/IEC (or if regionally required, the head of the medical institution) should be kept informed of such changes as required by local regulations. In these cases, the sponsor may be required to send a letter to the IRB/IEC and the Competent Authorities (or, if regionally required, the head of the medical institution) detailing such changes.

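### From Cycle 2, Section 9.5.1.5.3 requires chemistry and hematology review before dispensing while Table 4 footnote p allows it up to 48 hours afterwards, and no text says which governs

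*Protocol*

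**What the plan says.** Protocol Section 9.5.1.5.3 (Laboratory Measurements) covers hematology, blood chemistry, urinalysis and pregnancy tests. It wants samples taken before dosing and "results reviewed prior to administration/dispensing of study drug at the beginning of each treatment cycle". It makes no exception for later cycles, and it sends clinically significant laboratory abnormalities to Table 2.

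Footnote p of Table 4 (Section 9.5.2.1) covers chemistry and hematology only. It requires review before the first dose on Cycle 1 Day 1 (C1D1), but only "within 48 hours after dispensing lenvatinib for all subsequent cycles". The same footnote says that, for a clinically relevant toxicity of Grade 3 or higher in these tests, sites must "repeat laboratory test and AE assessment at least every 3 days".

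Table 2 (Section 9.4.1.1) sets the action that depends on the results. For treatment-related toxicity, "Interruption for Grade 3 toxicities is mandatory" (footnote c). Footnote e exempts laboratory values that the investigator judges not clinically relevant. Grade 4 leads to discontinuation, with an exception in footnote g: "Excluding laboratory abnormalities judged to be non-life-threatening, in which case manage as Grade 3".

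**The concern.** The tests are the same and so are the cycles, but the deadlines differ. A review made 24 hours after dispensing in Cycle 3 is on time under footnote p and late under Section 9.5.1.5.3. Neither the site nor the monitor can tell from the protocol whether it is a deviation.

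The check is also one that dosing decisions depend on. From Cycle 2, full chemistry and hematology are scheduled only on Day 1 of each 28-day cycle; Cycle 2 Day 15 adds liver function alone. If the Day 1 result calls for interruption under Table 2, late review means that the subject keeps taking lenvatinib in the meantime. The repeat testing in footnote p may also start up to 48 hours later.

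**Working it through.** There is no planned figure to reproduce. The check is a comparison of texts, followed by a count of doses.

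**Side by side**

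| Occasion | Section 9.5.1.5.3 | Table 4 footnote p |
|---|---|---|
| C1D1, chemistry and hematology | before administration/dispensing | before administration |
| Day 1 of Cycle 2 onward, chemistry and hematology | before administration/dispensing | up to 48 hours after dispensing |
| Urinalysis and pregnancy test | before administration/dispensing | not addressed |

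The texts agree for C1D1. They conflict from Cycle 2, for chemistry and hematology only. The slash in Section 9.5.1.5.3 does not help: review 48 hours after dispensing is later than dispensing and, with daily dosing, also later than at least one administration.

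**Does any other text reconcile them?**

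- Section 9.5.1.5.3 cites Table 4 for the visits and time points at which samples are collected. It also allows laboratory assessments to be conducted according to Table 4. Neither statement concerns when results are reviewed.
- Section 9.5.2.2 refers to Table 4 "for a description and timing of each procedure and assessment". This is general and sets no precedence. It also speaks of prerandomization and randomization phases, which this single-arm trial does not have.
- Footnote b of Table 4 sets a 72-hour window for doing the tests, not for reading them.
- Section 9.5.1.5.1 makes it the responsibility "of the investigator to review all laboratory findings in all subjects", but gives no deadline.

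None of these resolves the conflict.

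**Extra doses under the later deadline**

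Inputs: once-daily dosing (Section 9.4.5); latest review 48 hours after dispensing (footnote p); blood draw up to 72 hours before the visit (footnotes b and p). Assumptions: no dose interruption, dispensing at the visit, and each window used in full.

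- Dispensing to review under footnote p: 48 h / 24 h = about 2 doses. Three would fit only if doses were taken exactly at both ends of the window.
- Dispensing to review under Section 9.5.1.5.3: 0 doses.
- Draw to visit, allowed under either deadline: 72 h / 24 h = about 3 doses.
- Longest time from draw to review: 72 h (about 3 doses) under Section 9.5.1.5.3, against 72 + 48 = 120 h (120 / 24 = about 5 doses) under footnote p.

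Only the two doses after dispensing are in dispute.

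**The case against.** The strongest reply is that the footnote is deliberate and governs. It separates C1D1 from all later cycles, which looks like an operational rule, while Section 9.5.1.5.3 is one sentence covering four kinds of test. Section 9.5.2.2 sends readers to Table 4 for timing, and Section 9.5.1.5.3 itself defers to Table 4 for conducting the tests. That reading is plausible, and it means that nobody can say from the documents which text is the mistake. It does not remove the conflict, because no sentence gives the schedule precedence and Section 9.5.1.5.3 is itself specific about the tests and about each cycle.

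Three further points stand and limit the concern:

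- A site can comply with both texts by reviewing before dispensing. A reader might infer that sites are forced into a deviation; they are not.
- A reader might infer that any Grade 3 laboratory value reviewed late means dosing through a mandatory interruption. Table 2 does not say that. The toxicity must be treatment-related, and values judged not clinically relevant are exempt. Harm needs late review, a Grade 3 or higher value, clinical relevance and relatedness to lenvatinib, all together.
- The protocol already tolerates delays of similar length. Blood may be drawn 72 hours before the visit, visits may move by 3 days, and for dipstick proteinuria of 2+ or more lenvatinib continues while a 24-hour collection is obtained within 72 hours.

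**Conclusion.** The inconsistency is real and confined to chemistry and hematology review from Cycle 2 onward. Its size is about two further daily doses before a qualifying abnormality is acted on, assuming uninterrupted dosing and review at the last moment that footnote p allows. This adds to a draw-to-visit interval of up to 72 hours that exists in any case.

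The documents give no frequency for late review or for qualifying Day 1 abnormalities, so no number of affected subjects can be stated. A reader might go on to infer an effect on response, survival or the power of the trial. Nothing supports that: the response and survival analyses do not depend on when a laboratory result is read, and the SAP needs no change. This is a low-severity point of safety-monitoring consistency, worth correcting because two instructions to sites should not disagree.

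**What to change.** Amend footnote p so that chemistry and hematology results are reviewed before administration on C1D1 and before dispensing on Day 1 of every later cycle, in line with Section 9.5.1.5.3. This is practicable: local laboratories run the tests, and blood may already be drawn up to 72 hours before the visit. The downside is less scheduling flexibility, and possibly an earlier draw or later dispensing where same-day results are not available. The documents give no laboratory turnaround time, so that burden cannot be sized.

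If the sponsor does intend the 48-hour allowance, the alternative is to write it into Section 9.5.1.5.3 for chemistry and hematology from Cycle 2, leaving urinalysis and pregnancy-test review as they are.

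Either way one sentence changes, and no samples or analyses are added. Section 11.1 sets the route: "Any change to the protocol requires a written protocol amendment or administrative change", approved by the sponsor. If the change is classed as an amendment specifically affecting subject safety, that section also calls for submission to health or regulatory authorities and for ethics approval. It could reasonably be combined with the next amendment.

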9.5.2.2 Description of Procedures/Assessments Schedule

Refer to [Table 4](#) for a description and timing of each procedure and assessment in the Prerandomization and Randomization Phase.

9.5.3 Appropriateness of Measurements

All clinical assessments are standard measurements commonly used in studies of RR-DTC. The safety assessments to be performed in this study, including hematology analyses, blood chemistry tests, urinalysis, radiologic studies, and assessment of AEs, are standard evaluations to ensure subjects safety.

9.5.4 Reporting of Serious Adverse Events, Pregnancy, and Events Associated with Special Situations

9.5.4.1 Reporting of Serious Adverse Events

All SERIOUS ADVERSE EVENTS, regardless of their relationship to study treatment, must be reported on a completed SAE form by email or fax as soon as possible but no later than 24 hours from when the investigator becomes aware of the event.

Serious adverse events, regardless of causality assessment, must be collected through the last visit and for up to 28 days after the subject's last dose. All SAEs must be followed to resolution or, if resolution is unlikely, to stabilization. Any SAE judged by the investigator to be related to the study treatment or any protocol-required procedure should be reported to the sponsor regardless of the length of time that has passed since study completion.

The detailed contact information for reporting of SAEs is provided in the Investigator Study File.

For urgent safety issues, please ensure all appropriate medical care is administered to the subject and contact the appropriate study team member listed in the Investigator Study File.

It is very important that the SAE report form be filled out as completely as possible at the time of the initial report. This includes the investigator's assessment of causality.

Any follow-up information received on SAEs should be forwarded within 1 business day of its receipt. If the follow-up information changes the investigator's assessment of causality, this should also be noted on the follow-up SAE form.

Preliminary SAE reports should be followed as soon as possible by detailed descriptions including copies of hospital case reports, autopsy reports, and other documents requested by the sponsor.

The investigator must notify his/her IRB/IEC of the occurrence of the SAE in writing, if required by their institution. A copy of this communication must be forwarded to the sponsor to be filed in the sponsor's Trial Master File.

9.5.4.2 Reporting of Pregnancy and Exposure to Study Drug Through Breastfeeding

Any pregnancy in which the estimated date of conception is either before the last visit or within 28 days of last study treatment, or any exposure to study drug through breastfeeding during study treatment or within 28 days of last study treatment, must be reported.

If an adverse outcome of a pregnancy is suspected to be related to study drug exposure, this should be reported regardless of the length of time that has passed since the exposure to study treatment.

A congenital anomaly, death during perinatal period, an induced abortion, or a spontaneous abortion are considered to be an SAE and should be reported in the same time frame and in the same format as all other SAEs (see Reporting of Serious Adverse Events [Section 9.5.4.1]).

Pregnancies or exposure to study drug through breastfeeding must be reported by fax or email as soon as possible but no later than 1 business day from the date the investigator becomes aware of the pregnancy. The contact information for the reporting of pregnancies and exposure to study drug through breastfeeding is provided in the Investigator Study File. The Pregnancy Report Form must be used for reporting. All pregnancies must be followed to outcome. The outcome of the pregnancy must be reported as soon as possible but no later than 1 business day from the date the investigator becomes aware of the outcome.

A subject who becomes pregnant must be withdrawn from the study.

9.5.4.3 Reporting of Events Associated with Special Situations

9.5.4.3.1 REPORTING OF ADVERSE EVENTS ASSOCIATED WITH STUDY DRUG OVERDOSE, MISUSE, ABUSE, OR MEDICATION ERROR

Adverse events associated with study drug overdose, misuse, abuse, and medication error refer to AEs associated with uses of the study drug outside of that specified by the protocol. Overdose, misuse, abuse, and medication error are defined as follows:

Overdose	Accidental or intentional use of the study drug in an amount higher than the protocol-defined dose
Misuse	Intentional and inappropriate use of study drug not in accordance with the protocol
Abuse	Sporadic or persistent intentional excessive use of study drug accompanied by harmful physical or psychological effects

Medication error Any unintentional event that causes or leads to inappropriate study drug use or subject harm while the study drug is in the control of site personnel or the subject.

All AEs associated with overdose, misuse, abuse, or medication error should be captured on the Adverse Event CRF and also reported using the procedures detailed in Reporting of Serious Adverse Events ([Section 9.5.4.1](#)) even if the AEs do not meet serious criteria. Abuse is always to be captured as an AE. If the AE associated with an overdose, misuse, abuse, or medication error does not meet serious criteria, it must still be reported using the SAE form and in an expedited manner but should be noted as nonserious on the SAE form and the Adverse Event CRF.

9.5.4.3.2 REPORTING OF STUDY-SPECIFIC EVENTS

Study-specific events, consisting of clinically significant tumor bleeding or bleeding due to major artery invasion, should always be considered as serious important medical events, which will be entered on the Adverse Event CRF and reported using the procedures detailed in Reporting of Serious Adverse Events ([Section 9.5.4.1](#)), even if the study-specific event does not meet other serious criteria.

9.5.4.4 Expedited Reporting

The sponsor must inform investigators (or as regionally required, the head of the medical institution) and regulatory authorities of reportable events, in compliance with applicable regulatory requirements, on an expedited basis (ie, within specific time frames). For this reason, it is imperative that sites provide complete SAE information in the manner described above.

